4.1.5.2 Biomarker Research

Biomarker research will be aimed at identifying prognostic factors for patients with LMD, factors important for pembrolizumab therapy, and factors important for predicting response or resistance to pembrolizumab and other immunologic targets. Planned biomarker analyses are detailed in Table 2 below.

4.1.5.2.1. Genomic Correlates in CSF

CSF will be stored in 1 mL aliquots in cryovials, and flash frozen at -80C. Circulating tumor DNA will be assessed by Safe-SeqSwith primers and probes specific for tumor mutations as described above. CSF tumor cells will be isolated by microdissection. CSF will be collected as described in section 6.1.2.8.3.

Total circulating DNA is defined as the extracellular genome and mitochondrial DNA that is present in the CSF. It includes normal as well as mutant DNA and will be quantified by real-time PCR of a human LINE sequence. Additionally, size distribution of total circulating DNA will be determined by amplicons of varying lengths.

Due to low cellularity, a limited number of analyses can be done on CSF tumor cells. The presence of CSF-tDNA in patients with LMD has not been previously assessed at our institution. Depending on the number of tumor cells isolated and quantity of CSF-t-DNA available, we will assess: 1. Tumor cells and CSF-tDNA by next-generation sequencing, using described methods⁷³. From here, candidate neoantigens may be identified using a bioinformatics platform.

4.1.5.2.2 Genomic Correlates in Blood

Circulating tumor cells and cell-free DNA in serum obtained at pre-selected timepoints in this study, will be interrogated genomically. Circulating tumor cells and cfDNA will be obtained using methods described by [name] and colleagues. Depending on the number of tumor cells isolated and quantity of cf-DNA available, we will assess: 1. Tumor cells and cf-DNA by whole-exome sequencing, using methods outlined by [name] and colleagues⁶⁹, from here, candidate neoantigens may be identified using a bioinformatics platform.

Tumor-specific circulating DNA distinguishes from normal DNA by the occurrence of point mutations in tumor derived DNA. We will use Safe-SeqS, a next-generation sequencing assay that enables the detection of tumor specific DNA in a high background of normal DNA with high sensitivity and specify. In this study a panel of frequent point mutation or other genetic mutations specific for each tumor type is used to identify and monitor the fraction of tumor DNA. Tumor-specific circulating DNA as measured by the Safe-SeqS assay will be a continuous variable and shall be represented as a ratio between the mutant and wild-type allele evaluated. The development of techniques to analyze genetic alterations in blood of

patients is a rapidly changing field. The methods used to adequately detect mutated DNA and to differentiate it from wild type DNA will be adjusted and modified as appropriate on an ongoing basis. Total circulating DNA is defined as the extracellular genome and mitochondrial DNA that is present in the cell-free portion of the blood e.g. plasma or serum. It includes normal as well as mutant DNA and will be quantified by real-time PCR of a human LINE sequence. Additionally, size distribution of total circulating DNA will be determined by amplicons of varying lengths. We will also collect whole blood in 2x10 mL plasma preparation tubes with EDTA (PPT, BD Vacutainer, Franklin Lakes, NJ) and gently swirl tubes to mix blood with EDTA. Within two hours of collection, the sample will be processed using standard procedures for plasma separation. Plasma will be divided into 1 ml aliquots and stored at -80 degrees C. Pellets from this separation procedure will be washed in PBS and then divided into aliquots and also stored at -80C. These samples will be collected as detailed in section 6.1.2.8.2

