3.3 Exploratory Objectives

(1) To determine whether genomic markers can be detected in the CSF of patients with LMD from solid tumors, as detailed in section 4.1.5.2.

- (2) To investigate potential associations between genomic markers in the CSF and CNS/systemic tumor burden, clinical outcomes, and genomic markers in the serum, before and after pembrolizumab therapy, as detailed in section 4.1.5.2.
- (3) To determine whether immune cells can be detected in the CSF of patients with LMD, before and after pembrolizumab, as detailed in section 4.1.5.2.
- (4) To investigate potential associations between markers of immune activation on cells in the CSF, and clinical outcomes or response to pembrolizumab, as detailed in section 4.1.5.2.

Hypothesis: CSF t-DNA will be detectable in the CSF of patients with LMD. CSF t-DNA levels may correlate with tumor burden, clinical outcomes, or response to pembrolizumab therapy.

Hypothesis: Immune cells will be detectable in the CSF of patients with LMD, before and after pembrolizumab.

Hypothesis: Markers of immune activation on tumor or immune cells in the CSF will predict for improved clinical outcomes or response to pembrolizumab.

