6.1.2.8.3. CSF Sample collection

Patients will undergo a lumbar puncture using routine clinical care procedures to collect up to 10-15cc of CSF for research purposes, after routine clinical CSF is obtained. In patients with a CSF-access device such as an Ommaya reservoir or shunt reservoir, the study team may use this device to obtain CSF as an alternative to lumbar puncture. A CSF sample will be obtained during screening to obtain a "baseline" sample, and assess for eligibility based on CSF cytology. In patients who proceed with the study, repeat CSF samples will be obtained prior to administration of cycle 3 of therapy and 2-3 weeks after administration of cycle 4 (if last treatment, as end-of-treatment sample) or prior to cycle 5, if the patient is planned to receive cycle 5. The maximum number of lumbar punctures from an individual patient is four. In order to safely complete an LP for the acquisition of a CSF sample, patients must:

- a) Have an ECOG performance status < 2
- b) Have normal laboratory criteria as defined below:
- -Platelets >100,000/mcL[SEP]
- -PTT above institutional limits
- -INR above institutional limits
- c) No clinical or radiographic evidence of elevated intracranial pressure (such as papilledema, obstructive hydrocephalus, or signs of herniation).
- d) Not be taking blood-thinning products such as clopidogrel, low-molecular weight heparin, or coumadin.
- 5) For patients undergoing an LP, no history of LP complication such as hematoma, infection, herniation, or blood patch, and a complicated LP procedure in the past.

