Secondary endpoints will include CNS-PFS, OS and safety. Kaplan-Meier curves will be used to assess CNS-PFS and OS. Cause of death will be recorded. Safety will be assessed as detailed above, and monitored as per JHH SKCCC Data Safety and Monitoring Plan. Exploratory endpoints will include genomic testing of tumor cells and cell-free DNA in CSF and serum, and immunologic studies of immune cells in CSF and serum at pre-defined timepoints. These data will be presented descriptively. Genomic and immunologic correlates from available tissue in selected patients, will be presented descriptively. Means and standard deviations of all markers will be computed and 95% confidence intervals will be constructed. For serum markers, linear regression model (with proper transformation of the data) will be used to compare slopes in repeated measures between pre-defined time-points. Our institution sees 250 new patients per year with advanced lung cancer, 5% of which will have LMD (n=18 in 18 months), 200 new patients with breast cancer, 5% of which will have LMD (n=15 patients in 18 months), and selected patients with other solid tumors per year with LMD (n=10 per year), not including patients in follow-up. Taking into account that this may be a less fit patient population, we conservatively estimate that we will accrue 1 patient per month at our institution and 1 additional site that have agreed to participate in the study. Study duration will be approximately 24 months, allowing 18 months for accrual and 6 months for follow-up and data analysis.

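### The only stated tumor-DNA scale is a mutant/wild-type ratio, and no within-patient change is specified for CSF markers, so either summary can move without a change in tumor DNA

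*Combined protocol and SAP*

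**What the plan says.** Section 4.1.5.2.2 (blood) makes the Safe-SeqS result a continuous variable that "shall be represented as a ratio between the mutant and wild-type allele evaluated". Section 4.1.5.2.1 (CSF) names the same assay: "Circulating tumor DNA will be assessed by Safe-SeqSwith primers and probes specific for tumor mutations as described above". It gives no scale of its own. Both sections also plan a total-DNA measurement; in the CSF section, "It includes normal as well as mutant DNA and will be quantified by real-time PCR of a human LINE sequence". Neither says that the total will be combined with the ratio.

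Section 7.2.1 sets out the analysis: "Means and standard deviations of all markers will be computed and 95% confidence intervals will be constructed". A model over time follows, for one fluid only: "For serum markers, linear regression model (with proper transformation of the data) will be used to compare slopes in repeated measures". For CSF markers there is no within-patient change, no model and no rule for missing samples. The biomarker results are to be descriptive.

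Section 3.3, objective 2, looks for associations of genomic markers in CSF with tumor burden and clinical outcomes, before and after treatment. The attached hypothesis is that "CSF t-DNA levels may correlate with tumor burden, clinical outcomes, or response to pembrolizumab therapy".

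**The concern.** The denominator of the ratio is normal DNA. Immune cells are one source of it, and the trial studies them in CSF before and after pembrolizumab because treatment may alter them. A change in the ratio on treatment therefore cannot by itself distinguish a change in tumor DNA from a change in background DNA. The serum slope model does not help, because it would be fitted to the same ratio.

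The second issue is who contributes a follow-up CSF sample. Section 4.1.4.5 puts median survival at 3 to 6 months. Section 4.9 ends participation at CNS progression, Section 4.9.2 allows no replacement, and Section 6.1.2.8.3 requires patients to "Have an ECOG performance status < 2" for a lumbar puncture. Later samples will probably come from the fitter patients. If the summaries are read as means before and after treatment, they compare different groups of patients.

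What is at stake is the reading of objective 2 and the CSF tumor-DNA hypothesis. A mean with a 95% interval before and after drug will be read as a drug effect even when it is labelled descriptive.

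**Working it through.** **The plan's own figure.** No figure is given for the biomarker analysis. The ceiling on marker pairs comes from Section 7.2.1: 16 analyzable patients and a 10% allowance, 16/0.9 = 17.8, rounded up to 18. This agrees with the plan.

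**Step 1: the ratio.** Let M be mutant DNA, W wild-type DNA and R = M/W. Hold M fixed and multiply W by f. R is then multiplied by 1/f.

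| Wild-type DNA | Change in ratio, tumor DNA constant |
|---|---|
| x0.5 | +100% |
| x1.5 | -33% |
| x2 | -50% |
| x3 | -67% |
| x5 | -80% |

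The factors are illustrations; the documents give no size or direction for a change in wild-type DNA.

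**Step 2: what total DNA adds.** With total T = M + W, the mutant fraction is R/(1+R) and M = T x R/(1+R). Take M = 0.05 and W = 1:
- Before: T = 1.05, R = 0.05, so M = 1.05 x 0.05/1.05 = 0.05.
- After W doubles: T = 2.05, R = 0.025, so M = 2.05 x 0.025/1.025 = 0.05.

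The absolute amount is unchanged while the ratio has halved. The total itself rises by 2.05/1.05 = 1.95. This assumes that the LINE result is calibrated to copies per mL in the same units as the allele counts.

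**Step 3: how many remain.** Assume exponential survival at the medians in Section 4.1.4.5, with 3 months = 13.04 weeks and 6 months = 26.1 weeks. CSF is due at about week 6 (before cycle 3) and week 12 (after cycle 4).
- Week 6: 73% to 85% alive, or 11.6 to 13.6 of 16.
- Week 12: 2^(-12/13.04) = 53% to 2^(-12/26.1) = 73% alive, or 8.5 to 11.6 of 16.

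**Step 4: effect on the mean.** Suppose log tumor DNA has correlation rho with the propensity to be lost, and a fraction p is retained. The retained mean shifts by -rho x phi(z)/p standard deviations, where z is the normal quantile of p and phi the normal density. With rho = 0.5:
- p = 0.529: z = 0.073, phi = 0.398, shift = -0.5 x 0.398/0.529 = -0.376 SD.
- p = 0.727: z = 0.604, phi = 0.332, shift = -0.5 x 0.332/0.727 = -0.23 SD.

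If the SD is 1 log10, the apparent falls are 1 - 10^(-0.376) = 58% and 1 - 10^(-0.23) = 41%, with no change in any patient.

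**Step 5: range.** Simulation used 20,000 runs of 16 patients, no average within-patient change, natural-log SD 1.0 to 1.5 and within-patient noise SD 0.3.

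| Retained of 16 | rho | Unpaired geometric-mean ratio | Paired ratio |
|---|---|---|---|
| 8 to 12 | 0.3 to 0.7 | 0.45 to 0.89 | 1.00 |
| 12 to 14 | 0.3 to 0.7 | 0.66 to 0.94 | 1.00 |
| 8 to 14 | 0 | 1.00 | 1.00 |

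**The case against.** Much of the case on the other side stands.

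- **Unpaired means.** A reader might infer that the plan has chosen unpaired CSF means at each time point. It has not: Section 7.2.1 says neither that the means are unpaired nor that they are taken by time point. The CSF summary over time is unspecified, and that is all that can be said.
- **Ratio in CSF.** The ratio sentence is in the blood section. The CSF section points to a description above it, whereas the ratio is defined below it. Applying the ratio to CSF is the natural reading, since no other scale is offered, but it remains an inference.
- **Direction.** A reader might infer that the ratio will mimic a response to pembrolizumab. Section 3.3 expects immune cells to be detectable before and after treatment; it does not predict a rise. The total-DNA measure is of extracellular DNA, so more intact cells need not mean more wild-type DNA, and a fall would bias the ratio upward.
- **Who is sampled.** The performance-status limit applies to lumbar puncture. Section 6.1.2.8.3 allows an access device instead, Section 6.1.4.1 asks for final-visit activities at early discontinuation, and Table 7 marks a CSF sample there, although its footnote 7 describes that sample only for patients completing four doses. Some patients leaving early may be sampled.
- **Survival.** Entry requires ECOG 0 to 1, so survival may be better than the general 3 to 6 months.
- **Choice of scale.** A per-mL value depends on sampling site and dilution; a ratio is internally normalised. This is a good reason to keep the ratio and report both.

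The descriptive label does not answer the point. A descriptive mean can still be confounded, and the planned total-DNA assay protects against misreading only if it is used.

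**Conclusion.** The concern holds in a limited form. The only defined tumor-DNA scale responds to wild-type DNA in either direction; the size is exact arithmetic once a factor is assumed (-50% for a doubling). CSF markers lack the repeated-measures treatment given to serum, so a fall in their mean could arise from selective loss alone. Its size rests on assumed correlation, SD and survival: a geometric-mean ratio of 0.45 to 0.89 across the range examined for 8 to 12 retained patients, and no effect if loss is unrelated to the marker.

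The documents do not support the stronger conclusion that both choices bias the results toward an apparent molecular response. Nor do they show that all the CSF objectives are affected: objective 1 asks about detection and objective 4 about immune-activation markers. The point bears mainly on objective 2 and the CSF tumor-DNA hypothesis. The primary endpoint and the sample size are untouched.

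**What to change.** In Sections 4.1.5.2.1, 4.1.5.2.2 and 7.2.1:

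1. State the scale for CSF explicitly. In both fluids, report mutant copies per mL, computed as R/(1+R) times LINE-quantified total DNA, beside the ratio. For CSF, record whether the sample came from lumbar puncture or a device.
2. Summarise CSF markers as within-patient change from baseline, on the log scale where suitable, in patients with both samples.
3. At each time point give the number sampled and the reasons for missing samples, and show baseline values for patients with and without follow-up CSF.

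The cost is SAP wording and a little more descriptive analysis; the samples and assays are already planned. Pairing removes the change in case mix but not all bias from informative loss: patients whose tumor DNA was rising when they were lost still drop out of the paired set. Item 3 lets the reader judge how serious that is.

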4.1.5.2.3. Immunologic Correlates in CSF

Due to low cellularity, a limited number of analyses can be done on CSF immune cells. Depending on the number of cells available, analyses will include but may not be limited to: 1. Quantify the numbers of activated immune cells in the CSF by isolating immune cells with cytospin or flow cytometry, and then performing multi-color immunofluorescence with CD3 and additional immune markers such as PD-1, TIM-3, LAG-3. 2. We will assess immune activation markers present in the CSF and multiplex immune cytokine analyses.

4.1.5.2.4 Immunologic Correlates in Blood

PBMCs and serum will be banked first, and analyses will be prioritized depending on numbers of cells available for analysis and CSF findings. Planned analyses may include but may not be limited to: 1. T-cell phenotyping of peripheral blood lymphocytes (PBLs) evaluated by multi-color flow cytometry for selected immune markers 2. Immune ligand expression of PBLs explored using multi-color flow cytometry 3. Soluble immune factors using ELISA 4. Antigen-specific T-cells using MHC-multimer assays.

4.1.5.2.5 Tumor Tissue Analyses

Archival tissue, pre-treatment biopsy tissue or on-treatment biopsy tissue will be analyzed in patients where this tissue is available. From a genomic perspective, analyses from available tumor cells may include but may not be limited to: next generation sequencing of tumor and matched normal tissue, this will define the genomic landscape of these tumor cells. Candidate neoantigen determination using a bioinformatics platform. From an immunologic perspective, analyses from available tumor cells may include but may not be limited to by immunohistochemistry using monoclonal antibodies for immune checkpoint ligands and TIL populations, immune ligand expression of TILs using multi-color flow cytometry, assessment of soluble immune factors in the tumor microenvironment, and assessment for the presence of antigen-specific T-cells using MHC-multimer assays. Analyses will be prioritized depending on the amount of tissue available for analysis.

Table 2: Biomarker Analysis Table

	Pre-Tx	C1D1	C2D1	C3D1	C4D1	Post-4	Co-Investigators/					
						cycles	Site of Testing					
Pembrolizumab		X	X	X	X							
	Biospecimen collection for analysis											
CSF X X X												
PBMCs/Serum	X			X		X						
Tumor tissue*	X*											
Γ	Cumor correl	ates (seru	ım +/- tum	or tissue*	if availabl	e)						
Cell-free DNA	X			X		X	[name]/					
							[name] Lab					
Immune activation*	X*						[name] Lab					
	T-cell corre	lates (PB)	Ls +/- tum	or TILs* i	f available	·)						
Immune activation in PBLs	X			X		X	[name] Lab					
Immune activation in	X*						[name] Lab					
TILs*												
	CSF analysis	(tumor c	ells, CSF-	tDNA, in	mune cell	s)						
CSF tumor cells	X			X		X	[name]/					
							[name] Lab					
CSF- tDNA	X			X		X	[name]/					
							[name] Lab					
CSF immune correlates	X		-	X		X	[name] Lab					

METHODOLOGY

- 4.2 Patient Sample
- **4.2.1** Sample Size: The accrual objective for this study is 18 eligible and evaluable patients
- **4.2.2 Accrual Rate**: The expected accrual rate for this study is approximately 1 patient per month
- **4.2.3 Gender:** Male and Female subjects
- **4.2.4** Race: Minorities will be actively recruited.
- **4.2.5 Diagnosis/Condition for Entry into the Trial:** Patients with advanced solid tumors

4.2.6 Subject Inclusion Criteria

In order to be eligible for participation in this trial, the subject must:

- 1. Be willing and able to provide written informed consent for the trial.
- 2. Be \geq 18 years of age on day of signing informed consent.
- 3. Patients with a histologically or cytologically confirmed solid tumor malignancy.
- 4. Cytologically-confirmed LMD or radiologically detectable LMD defined as either/or:
 - A) A measurable lesion on contrast-enhanced MRI of either the Brain or Total-Spine >3mm that has not been radiated within the last 3 months prior to commencement of study therapy.
 - B) Positive CSF cytology as defined in section 6.1.2.7.
- 5. Patients may be newly diagnosed or have received any number of lines of prior anticancer therapy. However, patients are required to have received available therapies for their primary disease, as deemed appropriate by the treating investigator.
- 6. Non-escalating steroid requirement at the time of consent and study drug initiation for the treatment of CNS symptoms.
- 7. Local radiation therapy (RT) is allowed as needed to manage symptoms appropriately, as long as there remains a measurable lesion in the CNS.
- 8. Whole-brain RT may be used, without a pre-defined washout period, prior to commencement of study therapy if the lesion that has been radiated is not the sole measurable lesion, or the patient is eligible based on positive CSF cytology.

- 9. Patients may continue therapy with a targeted agent if CNS disease developed while receiving the agent, and for defined regimens that have been deemed safe when combined with anti-PD-1 therapy.
- 10. Be willing to provide tissue from an archival tissue specimen in selected patients, where available.
- 11. Have a performance status of 0-1 on the ECOG Performance Scale.
- 12. Demonstrate adequate organ function as defined in Table 3, all screening labs should be performed within 10 days of treatment initiation.

Table 3. Adequate Organ Function Laboratory Values

System	Laboratory Value				
Hematological					
Absolute neutrophil count (ANC)	≥1,500 /mcL				
Platelets	≥100,000 / mcL				
Hemoglobin	≥9 g/dL or ≥5.6 mmol/L without transfusion or EPO dependency (within 7 days of assessment)				
Renal					
Serum creatinine OR Measured or calculated ^a creatinine	≤1.5 X upper limit of normal (ULN) OR				
clearance (GFR can also be used in place of creatinine or CrCl)	≥60 mL/min for subject with creatinine levels > 1.5 X institutional ULN				
Hepatic					
Serum total bilirubin	≤ 1.5 X ULN OR				
	Direct bilirubin ≤ ULN for subjects with total bilirubin levels > 1.5 ULN				
AST (SGOT) and ALT (SGPT)	≤ 2.5 X ULN OR ≤ 5 X ULN for subjects with liver metastases				
Albumin	>2.5 mg/dL				
Coagulation	·				
International Normalized Ratio (INR) or Prothrombin Time (PT)	≤1.5 X ULN unless subject is receiving anticoagulant therapy as long as PT or PTT is within therapeutic range of intended use of anticoagulants				
Activated Partial Thromboplastin Time (aPTT)	≤1.5 X ULN unless subject is receiving anticoagulant therapy as long as PT or PTT is within therapeutic range of intended use of anticoagulants				
^a Creatinine clearance should be calculated	per institutional standard.				

- 13. Female subject of childbearing potential should have a negative urine or serum pregnancy within 72 hours prior to receiving the first dose of study medication. If the urine test is positive or cannot be confirmed as negative, a serum pregnancy test will be required.
- 14. Female subjects of childbearing potential (Section 4.8.2) must be willing to use an adequate method of contraception as outlined in Section 4.8.2 Contraception, for the course of the study through 120 days after the last dose of study medication.

Note: Abstinence is acceptable if this is the usual lifestyle and preferred contraception for the subject.

15. Male subjects of childbearing potential (Section 4.8.2) must agree to use an adequate method of contraception as outlined in Section 4.8.2- Contraception, starting with the first dose of study therapy through 120 days after the last dose of study therapy.

Note: Abstinence is acceptable if this is the usual lifestyle and preferred contraception for the subject.

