4.6.1 Acceptable Concomitant Medications

All treatments that the investigator considers necessary for a subject's welfare may be administered at the discretion of the investigator in keeping with the community standards of medical care. All concomitant medication will be recorded on the case report form (CRF) including all prescription, over-the-counter (OTC), herbal supplements, and IV medications

and fluids. If changes occur during the trial period, documentation of drug dosage, frequency, route, and date may also be included on the CRF.

Palliative and supportive care is permitted during the course of this trial for underlying medical conditions and the management of symptoms. Major surgery for tumor control or symptom management is not permitted during the study or within 3 weeks of study commencement, as outlined in section 4.2.7. Palliative radiotherapy is permitted if considered medically necessary by the treating physician as long as the lesion is not the patient's sole measurable lesion on brain or spine MRI or a defined target lesion in the body by RECIST 1.1, as detailed in section 4.2.6. Trial therapy should be held during the course of palliative radiation, and should be resumed no early than the next schedules dose of trial therapy. The specifics of the radiation treatment given, including location, will be recorded. Additionally, patients who receive radiation therapy will be analyzed separately to assess the potential impact of radiation therapy on clinical outcomes.

All concomitant medications received within 28 days before the first dose of trial treatment and 30 days after the last dose of trial treatment should be recorded. Concomitant medications administered after 30 days after the last dose of trial treatment should be recorded for SAEs and ECIs as defined in Section 6.2.

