4.6.2 Prohibited Concomitant Medications

Subjects are prohibited from receiving the following therapies during the Screening and Treatment Phase (including retreatment for post-complete response relapse) of this trial:

- Antineoplastic chemotherapy
- Immunotherapy not specified in this protocol
- Chemotherapy not specified in this protocol
- Investigational agents other than pembrolizumab
- Radiation therapy
 - Note: Radiation therapy to a symptomatic lesion or to the brain may be allowed as per the inclusion criteria, detailed in section 4.6.1, or at the investigator's discretion.
- Live vaccines within 30 days prior to the first dose of trial treatment and while participating in the trial. Examples of live vaccines include, but are not limited to, the following: measles, mumps, rubella, varicella/zoster, yellow fever, rabies, BCG, and typhoid vaccine.
- Systemic glucocorticoids for any purpose other than to modulate symptoms from an event of clinical interest of suspected immunologic etiology. The use of physiologic doses of corticosteroids may be approved after consultation with the Sponsor.

Subjects who, in the assessment by the investigator, require the use of any of the aforementioned treatments for clinical management should be removed from the trial. Subjects may receive other medications that the investigator deems to be medically necessary.

The Exclusion Criteria describes other medications that are prohibited in this trial.

There are no prohibited therapies during the Post-Treatment Follow-up Phase.

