7.2. Statistical Analysis Plan

7.2.1 Statistical Plan

This is an open-label phase II study aimed at establishing the efficacy of single agent pembrolizumab, at the FDA-approved dose of 200mg every 3 weeks, in patients with solid

tumors and LMD. The primary endpoint will be CNS response at 12 weeks/after 4 cycles of therapy. The sample size is calculated with Clopper-Pearson's exact binomial confidence interval method. With 16 analyzable patients, defined as eligible patients who receive at least one dose of pembrolizumab, we determine that we will have an appropriate level of estimation accuracy for the first study of this experimental regimen. The following table summarizes the two-sided 90% exact confidence interval for different observed CNS response rate. Guarding against a 10% rate of patients either being ineligible or dropping out, the final sample size is 18 patients. If a higher rate of ineligible and drop-out rate is observed during the study conduct, the protocol may be amended to ensure at least 16 analyzable cases.

No. of patients with CNS response (%)	90% Confidence Interval for Observed CNS Response Rate (N=16)	
	Lower (%)	Upper (%)
1 (6.3%)	0.3	26.4
2 (12.5%)	2.3	34.4
3 (18.8%)	5.3	41.7
4 (25%)	9.0	48.4
5 (31.3%)	13.2	54.8
6 (37.5%)	17.8	60.1

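### As written, the primary CNS response rate can count the effect of recent or on-study CNS radiation as a response to pembrolizumab

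*Combined protocol and SAP*

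**What the plan says.** All references are to the combined protocol and SAP.

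- **Aim.** Section 7.2.1 describes a study "aimed at establishing the efficacy of single agent pembrolizumab". Section 4.4 calls the allocated treatment monotherapy.
- **Radiation before the trial.** Section 4.2.6, item 8: "Whole-brain RT may be used, without a pre-defined washout period, prior to commencement of study therapy". The sentence goes on to set a condition: the irradiated lesion must not be the only measurable one, or the patient must qualify on positive CSF cytology. Item 7 allows local radiation if a measurable CNS lesion remains. Item 4A requires an MRI entry lesion "that has not been radiated within the last 3 months prior to commencement of study therapy".
- **Radiation during the trial.** Section 4.6.1 permits palliative radiation that spares a sole measurable CNS lesion and the body target lesions. Section 4.6.2 lists radiation as prohibited, and says that subjects who need a listed treatment should leave the trial. The same list adds: "Radiation therapy to a symptomatic lesion or to the brain may be allowed as per the inclusion criteria", or at the investigator's discretion.
- **Planned handling.** Section 4.6.1: "patients who receive radiation therapy will be analyzed separately to assess the potential impact of radiation therapy on clinical outcomes". Section 7 does not mention this.
- **Response.** Section 7.2.4 accepts a reduction of measurable lesions on brain MRI, cytology clearance on two consecutive samples, or improved neurologic function. Where several criteria are available, the most easily assessed one is used.
- **Population.** Table 12 and section 7.2.1 include every eligible patient who received at least one dose.
- **Targeted agents.** Section 4.2.6, item 9: "Patients may continue therapy with a targeted agent if CNS disease developed while receiving the agent", for regimens considered safe with anti-PD-1 therapy.

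**The concern.** The safeguards on radiation act at two points: who may enter, and what may be irradiated. None acts at the third point, what counts as a response. A patient who qualifies on cytology can have whole-brain radiation shortly before day 1 with no lesion condition. If neurologic function then improves, or brain lesions shrink, section 7.2.4 scores a CNS response. The plan itself says in section 4.1.4.4 that radiation is used for bulky leptomeningeal disease thought to cause neurologic deficit, so neurologic improvement after radiation is a foreseeable event.

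Baseline imaging may be up to 28 days old (section 6.1.2.7.1), and the exception in section 4.6.2 covers screening as well as treatment. Radiation can therefore fall between the baseline scan and day 1, and its effect would then appear as change on study.

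At stake is what the primary rate means. With about 16 patients and no control arm, one or two responders change how the result is read.

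**Working it through.** **1. The plan's own figures.** Section 7.2.1: "With 16 analyzable patients, defined as eligible patients who receive at least one dose of pembrolizumab", then "Guarding against a 10% rate of patients either being ineligible or dropping out, the final sample size is 18 patients". 16 / 0.90 = 17.8, rounded up to 18, which agrees. Two-sided 90% Clopper-Pearson limits at N = 16 reproduce 11 of the 12 printed limits, for example 3/16 (5.3% to 41.7%) and 4/16 (9.0% to 48.4%). The exception is the upper limit for 6/16, printed as 60.1 and computed as 60.9; it does not affect this point.

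**2. Guards set against the response rule.**

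| Provision | What it restricts | Does it limit what counts as response? |
|---|---|---|
| 4.2.6 item 4A, 3 months without radiation | MRI entry lesion | No |
| 4.2.6 items 7 and 8 | Eligibility after radiation | No |
| 4.6.1, sole measurable lesion | Permission to irradiate | No |
| 4.6.1, separate analysis | An additional summary | No; the primary rate is unchanged |
| 7.2.4 | Definition of response | Silent on radiation |

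**3. Size.** The documents do not say how many patients will be irradiated. Inputs:

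- Irradiated patients: 2 to 4 of 16 (assumption).
- Response rate with radiation, from Table 1: 4/51 = 7.8% (whole-brain radiation, NSCLC; printed as 7%) and 8/26 = 30.8% (whole-brain radiation plus intrathecal methotrexate, so high for radiation alone).

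Extra responders = number irradiated × response rate, taking these patients as otherwise non-responders:

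- Low: 2 × 4/51 = 0.16; 0.16 / 16 = 1.0 percentage point.
- High: 4 × 8/26 = 1.23; 1.23 / 16 = 7.7 percentage points.

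**4. Effect on the observed count.** Let p be the true pembrolizumab response rate, f the irradiated share and b the response rate from radiation, acting independently. The apparent rate is p + f(1 − p)b. Take p = 5% (assumption) and f = 4/16 = 25%:

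- b = 7%: 0.05 + 0.25 × 0.95 × 0.07 = 6.7%.
- b = 31%: 0.05 + 0.25 × 0.95 × 0.31 = 12.4%.

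The chance of 3 or more responses in 16 is 4.3% without radiation, 8.6% at the lower value and 31.7% at the upper.

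**5. What a separate analysis could show.** With 4 irradiated patients, 2/4 has a 95% exact interval of 6.8% to 93.2%. In the other 12, 3/12 has 5.5% to 57.2%. Groups of this size cannot show how much of the overall rate is due to radiation.

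**The case against.** The strongest reply is that the plan has more protection than the separate analysis alone. Item 8 carries its lesion condition. Exclusion 14 (section 4.2.7) bars therapy that might confound the results. A tumor board reviews candidacy (section 4.2.8). Trial therapy is held during palliative radiation (section 4.6.1). New neurologic signs or symptoms after at least two cycles are progression (section 6.1.2.7), clinical progression overrides MRI or cytologic improvement (Table 8), and CNS progression ends participation (section 4.9). Much radiation given for new symptoms after cycle 2 would therefore follow a progression call.

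This stands, and it shrinks the on-study part. It does not reach radiation before day 1, or radiation for existing symptoms without progression. Exclusion 14 rests on the investigator's opinion, alongside criteria that expressly allow radiation.

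Four stronger readings are tempting, and the documents do not support them:

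- **Immortal-time bias in CNS-PFS and OS.** Radiation before day 1 is a baseline characteristic. For on-study radiation, no CNS-PFS or OS comparison by radiation status is specified; section 7.2.1 plans Kaplan-Meier curves, and Table 12 disclaims formal inference.
- **Unrecorded co-treatment.** Section 4.6.1 records the details and location of on-study radiation, and section 6.1.1.6.2 covers prior radiation.
- **Half or more of irradiated patients becoming responders.** The plan's own rates are about 8% and 31%.
- **Targeted agents as an equal source of false responses.** CNS disease must have developed on the agent, so a new CNS response to it is less likely. Monotherapy in section 4.4 can be read as describing only the allocated treatment. What remains is a mismatch with the single-agent description, which a descriptive tabulation meets.

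**Conclusion.** The point holds in limited form. The response rule in section 7.2.4 can credit radiation effects to pembrolizumab, and the separate analysis in section 4.6.1 does not prevent this. That analysis has no window, method or endpoint, and it is not carried into Section 7. It sits in a paragraph on on-study palliative radiation, so its reach to earlier radiation is unclear.

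The illustrated size is 1 to 8 percentage points, conditional on 2 to 4 irradiated patients in 16 and on the Table 1 rates. This is not a bound: section 4.1.4.4 warns that historical response definitions vary widely, and section 7.2.4 accepts any one of three routes. The shift is small beside the sampling interval (36.4 points wide for 3/16), but the interval does not reflect it. A reader might infer that a positive result would be uninterpretable; the documents do not support that, since neither the frequency nor the effect of radiation is known. The change is worth making because it is cheap.

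**What to change.** No change to eligibility or treatment is needed for the analysis.

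1. **Section 7.2.4.** Count a CNS response only if it is documented before any on-study CNS radiation. State whether the first or second negative sample dates a cytologic response.
2. **Denominator.** Keep every eligible treated patient in it, irradiated or not.
3. **One sensitivity analysis.** Score as non-responders patients with CNS radiation within 3 months before day 1. This borrows the window of item 4A, which is a rule for one lesion; applying it to the whole patient is a choice and should be stated as such. It also covers radiation between the baseline scan and day 1.
4. **One table.** Show response by radiation status (none, before day 1, on study) and, descriptively only, by continued targeted agent. Move the separate analysis of section 4.6.1 into Section 7 in this form.
5. **Consistency.** Sections 4.6.1 and 4.6.2 both prohibit and permit radiation and must be reconciled.

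The cost is SAP wording, one table, and a check that the case report form captures the dates and field of CNS radiation. The downside is that a true pembrolizumab response first seen after on-study radiation is not counted. The sensitivity rate is a conservative lower bound, because some patients scored as non-responders may have responded to pembrolizumab.
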